9.10 Participant privacy and confidentiality

The study staff will ensure that the participants' privacy is maintained.

No individual information will be collected at vaccination sites.

Pre- and post- survey participants will be identified by initials, age (and date of birth if known), sex and a unique ID number. All documents and electronic data will be stored securely and only accessible by study staff and authorized personnel. The study will make the information anonymous as soon as it is practical to do so.

The Investigator Site File and associated source documents will be retained for at least 10 years after the completion of the study. Written approval from the Sponsor will be obtained prior to destroying records.

All study related documents will be kept in locked cabinets at the study site. Filing cabinets with the study data and the participant information will be locked and accessed only by authorized persons from the Sponsor and Regulatory Authorities.

Participant personal data will be kept confidential and the privacy of all participants will be protected as far as permitted by law and following GDPR regulations. To ensure traceability and following

standard practice, nasopharyngeal samples will be labelled with participant initials, in addition to a unique ID number, sex and age. Only staff involved with the study conduct and local and international regulatory agencies may review these records.

10 Administrative aspects

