Safety analysis will be based on the entire study population. Safety and tolerability of PCV10 will be assessed by comparing the frequency (%) of AEs and SAEs in full-dose and fractional-dose arms to the control arm using the Fisher's exact test. Safety data will be presented in tabular and/or graphical

format and summarized descriptively. Data will be analyzed according to an intention-to-treat approach. In the unlikely event of clusters receiving incorrect interventions, or being only partially vaccinated, per-protocol analyses will be repeated on the primary endpoint.

13 Quality assurance and control

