3.1.4 Schedule of Study Visits and Procedures

During the baseline and 6 months post-vaccination surveys, one visit will be performed. No follow-up will be done after this visit. During the two surveys, a questionnaire will be filled for each selected household to collect socio-demographics information on the household, including the number of members who live in the household, their age and sex, school or other day care attendance of the children living in the household, PCV vaccination status of children living in the household, exposure to solid fuel smoke, and smoking habits.

For each selected child aged 1 to 9 years, an additional questionnaire will be filled to collect information on the child’s recent symptoms of an upper respiratory tract infection, including receiving any antimicrobials in the previous two weeks, and a nasopharyngeal sampling will be performed.

Additionally at baseline, on a selected household member, a social interactions questionnaire will be filled to collect information on the number of contacts with people of different age groups in the last 24h.

During the post vaccination survey, additional information on the PCV vaccination during the study campaign from all children of the targeted age group will be collected.

Vaccination activities will occur at village level and will take place on a pre-scheduled day. All children of the target age group for vaccination, for instance aged 1-9 years of age, residing in the study villages allocated to full or fractional dose arm will be targeted for vaccination. Vaccination will occur at fixed sites in each participating village. Vaccination activities will be timed to happen in the same geographical area at the same

time and will be scheduled as to not interfere with other planned vaccination activities. The number of doses of vaccine administered at each site will be noted on tally sheets.

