3.1.5 Analysis Populations

All data from the surveys will be analysed in an intent to treat approach, ie including all data collected in the household of each selected child. Only data collected in the households of selected children with results of the nasopharyngeal swab will be analysed for the primary outcome.

Analyses of the primary outcome will be repeated on the per protocol population. The per protocol population will include children that provided a NP sample and completed the child questionnaire as well as the household questionnaire and for which no protocol violation was reported and who were in clusters who received the intervention allocated during randomization.

Safety analysis will be conducted in two different groups depending on study intervention:

- In clusters allocated to the control arm, all children aged in the target age group for vaccination campaigns will be considered. The denominator in this study arm will be the population of the clusters according to the census records used to establish the sampling frame for the cluster.
- In clusters allocated to receive full- or fractional-dose mass campaigns, only children who actually received a vaccination will be considered, and the denominator in these study arms will be the number of children vaccinated based on records from the vaccination sites.

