4.3.2 Primary Analysis

4.3.2.1 Primary Analysis

The primary analysis is the test of the superiority of the full dose vaccination arm compared to the control arm, on the reduction in NP carriage. The reduction will be calculated by comparing the proportion of children carrying VT pneumococci 6 months post-vaccination to baseline, at the time of vaccination.

This primary analysis on the primary endpoint will be performed on the intent to treat population, using generalised estimating equations (GEE) to estimate risk differences and their associated 95% CI for the effect of the full dose vaccination on the reduction in VT carriage compared to the fractional dose. GEE will be used to account for clustering effect. Adjusted analyses with covariates (including but not limited to age, sex, vaccination coverage, time between baseline survey and vaccination, time between vaccination and follow-up survey, baseline prevalence of VT carriage) and stratification factor will be performed.

The administrative vaccination coverage for each site where vaccination campaign is performed, is obtained by the formula:

(number of vaccinees/number of expected children from the age group 1-9 years old) x 100.

The superiority will be tested at the 0.05 significance level.

For the non-inferiority analysis, the 95%CI around the risk difference in the proportion of children with VT carriage (full dose group – fractional dose group) will be using generalised estimating equations (GEE) and non-inferiority will be achieved if the lower limit of this 95%CI is >-7.5%.

Non inferiority analyses will be repeated on the per protocol population. Sensitivity analyses on the primary endpoint will be repeated by analyzing clusters according to the intervention they actually received if misallocation occurred.

In order to account for any potential seasonal variation seen due to timing of the surveys, additional sensitivity analyses will be performed, comparing the difference in prevalence between the full-dose and control arms, relatively to the reduction observed in the control group..

Multivariable logistic regression analyses will be performed to obtain adjusted estimates of risk factors for VT carriage at baseline and after vaccination campaign. The Odds Ratio and 95% CI will be adjusted for age and sex. Robust SE will be used to allow for clustering at the cluster level. 4.3.2.2 Secondary Analysis.

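### Safety data are grouped by the arm a cluster was allocated to, and no analysis by intervention received is planned if a cluster is given the wrong one

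*Combined protocol and SAP*

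**What the plan says.** SAP 3.1.5 defines two safety groups. For the vaccine arms, "In clusters allocated to receive full- or fractional-dose mass campaigns, only children who actually received a vaccination will be considered". Each vaccine arm is then divided by a count of vaccinees taken from site records. For control, every child of target age in a control-allocated cluster counts: "The denominator in this study arm will be the population of the clusters according to the census records". In both cases the cluster's allocation sets the arm.

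The plan provides for wrong interventions in three places:
- Protocol section 12 calls the event unlikely and responds with a per-protocol analysis of the primary endpoint. Just before this, in the same paragraph as the safety analysis, it says "Data will be analyzed according to an intention-to-treat approach".
- SAP 3.1.6 makes a wrong intervention a protocol violation at cluster level.
- SAP 4.3.2.1 adds an as-received analysis: "Sensitivity analyses on the primary endpoint will be repeated by analyzing clusters according to the intervention they actually received if misallocation occurred".

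SAP 4.3.3 compares each dose arm with control by Fisher's exact test. It has no as-received provision, and it bases safety on the whole study population, which does not match the vaccinees-only rule in 3.1.5 for the vaccine arms.

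**The concern.** Safety tables are read as statements about what a product did to those who received it. Under 3.1.5, if a fractional-allocated cluster were given full doses, its injection-site reactions, SAEs and deaths would appear in the fractional-dose column. If a control-allocated cluster were vaccinated, its children would remain in the unvaccinated comparator, and that comparator enters the planned tests. The SAP already accepts for carriage that results by intervention received are worth having after a misallocation. It omits the same step for safety, where grouping by what was received is the usual choice.

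The fractional arm carries a hazard that the protocol itself names (7.2.1 and 9.4): contamination linked to repeated puncture of the vial. The protocol considers that risk minimal. If it did occur, it could be concentrated in one vial or session, so the label on a single session could matter more than its share of the arm suggests.

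**Working it through.** **Inputs from the documents.** 27 clusters in each vaccine arm and 9 in control; an average of 2000 people per cluster; 30% of them aged 1-9 years; cluster populations from 500 to 4000 (protocol 7.1, SAP 3.1.1 and 3.1.3).

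**Plan's own figure.** 54 × 2000 × 0.30 = 32,400 children targeted, as stated. Per cluster: 2000 × 0.30 = 600. Per vaccine arm: 27 × 600 = 16,200. Control: 9 × 600 = 5,400.

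**Share of an arm under the wrong label.** This assumes equal vaccination coverage across clusters, so that targeted numbers stand in for vaccinees.
- One average cluster in a vaccine arm: 600/16,200 = 3.7%. Two: 7.4%. Three: 11.1%.
- Smallest and largest permitted clusters: 500 × 0.30 = 150 and 4000 × 0.30 = 1,200, giving 150/16,200 = 0.9% and 1,200/16,200 = 7.4%.
- One control cluster: 600/5,400 = 11.1%, with a range of 150/5,400 = 2.8% to 1,200/5,400 = 22.2%.

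**Effect on the tested comparison.** Suppose a share w of control received the same dose as the arm being compared. With event risks r1 (vaccinated) and r0 (unvaccinated), the control rate becomes (1 − w)r0 + w·r1. The observed difference is then (1 − w)(r1 − r0). At w = 11.1% the difference shrinks by 11.1%. SAP 3.1.4 describes control-arm collection for SAEs only, so this acts through SAEs and deaths.

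**Effect on the descriptive dose contrast.** The documents give no event rates. Assume 5% for full dose and 2% for fractional. If one full-allocated cluster receives the fractional dose, the full-arm rate by allocation is (15,600 × 0.05 + 600 × 0.02)/16,200 = 792/16,200 = 4.89%, against 5.00% by dose received. The difference falls from 3.00 to 2.89 points, a loss of 3.7%. Numerator and denominator move together here: the dose label is wrong, but the rate is internally consistent.

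**Children vaccinated at another arm's site.** No section says whether their events follow residence or vaccination site, so the result depends on an unstated rule.
- A fraction c crosses in each direction, with events and denominators both by residence: the observed difference is (1 − 2c) times the true one. For assumed c of 1%, 2% and 5%, the loss is 2%, 4% and 10%.
- 5% of full-arm residents (810) are dosed at fractional sites, with events by residence and denominators by site. The full-arm rate is (15,390 × 0.05 + 810 × 0.02)/15,390 = 5.105%. The fractional-arm rate is 324/17,010 = 1.905%. The ratio is 2.68 instead of 2.50. At 1% and 10% it is 2.54 and 2.87.

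The first pattern makes the doses look more alike and the second less alike.

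**The case against.** The strongest reply is that the situation is remote and would be visible. Sites lie within villages ("Vaccination will occur at fixed sites in each participating village"), so site, cluster and dose normally coincide. The residence criterion and the 2 km separation limit movement between clusters. Control villages receive no campaign, so the 11% figure needs a whole campaign to be held in the wrong place. A wrong intervention is logged as a violation, events are listed individually, and SAEs go to the DSMB. The average effect of one misdosed cluster is small, and full versus fractional is not formally tested for safety. All of this stands, and it limits the point to one that bites only if misallocation occurs. It does not supply the missing analysis. SAP 3.1.6 might allow a violating cluster to be excluded, but it names no such rule for a wrong dose, and exclusion would drop the events without assigning them to the dose given.

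A reader might infer more than the documents support:
- *That events and denominators are built on different keys.* This is an inference. A whole-cluster error causes no mismatch, and for a child vaccinated elsewhere the documents give no assignment rule at all.
- *That the bias always makes the two doses look alike.* It does not, as the two patterns above show.
- *That vaccination cards already hold what is needed.* Protocol 11.3 lists cards as source documents but does not say that they record dose or site. Protocol 9.10 says "No individual information will be collected at vaccination sites", the site record described is a count ("The number of doses of vaccine administered at each site will be noted on tally sheets"), and neither the minimum SAE report nor the SAP's AE/SAE data items include dose or site.
- *That vaccine-arm safety is plain intention-to-treat.* The protocol sentence is general, and SAP 3.1.5 restricts those arms to vaccinated children. The problem is the grouping by allocation, which 3.1.5 states on its own.

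**Conclusion.** The point holds in a limited form. Safety grouping follows cluster allocation, and every planned remedy for a wrong intervention stops at the carriage endpoint. If a cluster receives the wrong intervention, following the plan would report its safety events under a dose the children did not get, or leave vaccinated children in the control comparator used for testing. One average cluster amounts to about 3.7% of a vaccine arm or 11.1% of control, with ranges of 0.9% to 7.4% and 2.8% to 22.2% over the permitted cluster sizes. These shares rest on the planned cluster numbers, the 30% age share and equal coverage. The event rates and cross-over fractions above are assumptions. If no misallocation or cross-over occurs, nothing changes. The gap should still be closed before analysis, because the plan allows for the event and the correction is cheap.

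**What to change.** In SAP 3.1.5 and 4.3.3, and in protocol section 12:
- Make the main safety tabulations and tests by the intervention that the cluster or vaccination site actually delivered, with events and denominators keyed to the same site.
- Count a wrongly vaccinated control cluster as vaccinated.
- Keep the by-allocation table as a secondary display.
- Reconcile the safety population in 3.1.5 with the whole-population statement in 4.3.3 and protocol section 12.

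The cluster-level change needs wording only, since a wrong intervention is already recorded as a cluster violation. Children vaccinated outside their own cluster need a vaccination-site field on the AE/SAE form. The dose can then be attached centrally from the site, which avoids writing it on a card held in villages that are not told their allocation. The statistical cost is that, after a misallocation, the main safety groups are no longer exactly the randomised groups. The by-allocation table is kept for that reason.

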3.1.6. Protocol Violation and Deviations

A protocol violation is any departure from the approved protocol, trial documents or any other information relating to the conduct of the study, which may affect the safety of trial participants or the study outcomes. Examples include failure to obtain informed consent (i.e. no documentary evidence) or enrolment of children in one of the two surveys that do not meet inclusion/exclusion criteria.

Incorrect intervention provided during the vaccination will be considered as a protocol violation at the cluster level.

A protocol deviation is any departure from the approved protocol, trial documents or any other information relating to the conduct of the trial that does not result in harm to the trial participants and does not significantly affect the study outcomes. Examples of deviations include isolated incident of a missed or incomplete study procedure or study evaluation, cases of mis-randomization or mis-stratification will also be considered as a protocol deviation.

A final Protocol Deviation Listing will be generated and reviewed by sponsor personnel prior to freezing the database to ensure that all important deviations, including those that may lead to exclusion from analysis, are captured and summarized.

Participants or villages/clusters will be excluded entirely from analysis if they have a protocol deviation defined as a full exclusion that affects the validity of their data (e.g., failure to obtain informed consent).

3.2 Assessment of Objectives

3.2.1 Efficacy Assessments

3.2.1.1 Primary outcome

The primary outcome is the prevalence of vaccine-type NP carriage in children approximately 1 to 9 years of age. It will be assessed before vaccination campaign (baseline survey) and at 6 months post PCV10 vaccination campaign (post vaccination survey). VT pneumococci are defined as those covered by PCV10 (1, 5, 6A, 6B, 7F, 9V, 14, 19A, 19F, 23F).

3.2.1.2 Secondary outcomes

The secondary outcome is the prevalence of non-VT serotypes carriage in children approximately 1 to 9 years of age. It will be assessed as the same timepoints than for the primary outcome, ie during both surveys.

3.2.2 Safety Assessments

The safety outcomes are AE(s) at the injection site occurring within 7 days after vaccination and SAE(s) occurring within 28 days after the vaccination. SAEs from participants in clusters allocated to the control group will be collected during a period of time from the first vaccination date up to 28 days after the last vaccination date performed in clusters allocated to full or fractional dose, in the geographical area sharing the same health center.

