6.1 Definition of outcomes

Effect of PCV10 campaign

The effect of a single dose PCV10 campaign in the reduction of VT carriage will be assessed by: first, assessing the superiority of a campaign using full doses of PCV10 compared to control group without vaccination; and second, by establishing the non-inferiority of a campaign using fractional doses of PCV10 compared to a campaign using full doses.

NP carriage will be measured in the 3 study arms (full dose arm, fractional dose arm and control arm) in a baseline survey implemented prior to the vaccination campaign and in a post-vaccination survey conducted 6 months post-vaccination campaign.

The NP carriage of VT *S. pneumoniae* will be measured as the proportion of participants that are colonized with any of the 10 serotypes covered by PCV10 at each time point. The reduction in NP carriage will be calculated by comparing the proportion of children carrying VT pneumococci 6 months post-vaccination to baseline, at the time of vaccination. Prevalence of colonization of non-VT serotypes will also be described at both timepoints.

Vaccine safety

Vaccine safety will be monitored up to 28 days after vaccination and all AEs and SAEs will be recorded.

Cost-effectiveness and modelling study

An age-structured, dynamic, deterministic model of pneumococcal transmission will be constructed to estimate the impact of mass fractional dose PCV campaigns on VT carriage. The model will use the

data on social interactions between age groups and PCV coverage estimates collected during the baseline survey as well as the results of the VT carriage from the baseline survey.

Based on the modelled epidemiological impact of PCV10 mass campaigns, with both full and fractional doses, a cost-effectiveness analysis will be performed to estimate the incremental cost-effectiveness ratio of routine PCV10 mass campaigns.

The modelled epidemiological impact and cost-effectiveness of a fractional dose mass campaign will be used to inform ongoing discussions of dose-sparing strategies and the use of single-dose fractional PCV in acute humanitarian emergencies.

Facilitators and barriers to implementing mass campaigns of fractional dose PCV

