7.2.1 Summary of vaccine safety

The most frequently reported adverse reactions include fever, irritability, injection site reactions including pain, erythema, swelling or induration, decreased appetite, drowsiness and diarrhoea. Serious reactions are rare.

Extending the use of the 5-dose multi-dose vial to provide 25 administrations may increase the risk of injection site reactions e.g. swelling and localised inflammation due to contamination. The preservative contained in the vial should minimise this risk.

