7.13 Expected Results

The overall project will present results for each of the primary and secondary objectives. For the main trial, results of prevalence of vaccine-serotype pneumococcus will be presented and compared. The results of the qualitative study will be presented in the form of a report. All results will be communicated as described below in section 13.6.

8 Safety reporting for Adverse Events and Serious Adverse Event

Data on Adverse Events (AEs) will be collected in a passive surveillance system for 7 days following vaccination. Data on Serious Adverse Events (SAEs) will be collected in a passive surveillance system for 28 days following vaccination.

A health professional from the study team will be based in the nearest health centre to the vaccinated villages for 28 days after vaccination activities, and will be the key notifiers of AEs and SAEs to the study team. Moreover, the community health workers from the vaccinated villages will be asked to act as a focal point and communicate to the study team any events that occur during the follow-up period. During the vaccination activities, caretakers will be informed about vaccine safety and will be asked to contact the community health worker or to attend the nearest health centre in case of a health problem.

Following, the International Conference on Harmonization (ICH) Guidelines for Good Clinical Practice, an adverse event (AE) is defined as any untoward medical occurrence in a clinical trial subject to whom a vaccine has been administered; it does not necessarily have a causal relationship with the vaccine/vaccination.

Definitions of AEs and grading will be specified in an SOP. In this trial, the recording of AEs will be limited to the evaluation of injection-site reactions (pain, tenderness, induration, infection, etc).

A serious adverse event (SAE) is any untoward medical occurrence that:

- Results in death.
- Is life threatening: if the participant was at risk of death at the time of the event; it does not refer to an event that hypothetically might have caused death if it were more severe.
- Results in persistent or significant disability/incapacity: if the event results in a substantial disruption of the participant's ability to carry out normal life functions.

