4.3.3 Safety Analysis

Safety analysis will be based on the entire study population.

Any adverse events occurring within 7 days after vaccination, serious adverse events, or deaths will be summarized as n (%) of participants having experienced the AE(s), and SAEs or death by arms. Comparisons will be done between full-dose and fractional-dose arms with the control arm, using a Fisher's exact test.

All AEs will be coded to a "Preferred Term" (PT) and primary associated "System-Organ Class" (SOC) according to the MedDRA dictionary (Medical Dictionary for Regulatory Activities, version 25.0).

Counts and proportions will be provided overall and for each PT within each SOC. AE(s) will be tabulated overall and by grade, and by type of AEs:

- AEs non SAEs occurring with 7 days after vaccination
- SAEs
- SAEs leading to death

5. Statistical Tables to be Generated

<Consider appropriate tables for each of these categories and some examples are provided>

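### The plan gives both 28 days and 7 days as the window for recording adverse events; under the 7-day rule a non-serious injection-site infection starting on days 8–28 is not an outcome, although study staff are still in place.

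*Combined protocol and SAP*

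**What the plan says.** **The 7-day rule.** SAP 3.2.2 sets both windows in one sentence. It opens "The safety outcomes are AE(s) at the injection site occurring within 7 days after vaccination" and goes on to give 28 days for serious adverse events. Protocol section 8 applies the same limit at collection: "Data on Adverse Events (AEs) will be collected in a passive surveillance system for 7 days following vaccination". SAP 3.1.4 repeats it, and SAP 4.3.3 carries it into the tables with the category "AEs non SAEs occurring with 7 days after vaccination". The secondary objective on safety (protocol synopsis, protocol section 6, SAP 2.2) also gives 7 days for adverse events and 28 days for serious ones.

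**The 28-day statement.** Protocol 6.1, which defines the outcomes, says: "Vaccine safety will be monitored up to 28 days after vaccination and all AEs and SAEs will be recorded". It sets no shorter window for non-serious events.

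**Scope and staffing.** Protocol section 8 and SAP 3.2.2.2 restrict adverse events to injection-site reactions and list infection among them. On staffing, section 8 says: "A health professional from the study team will be based in the nearest health centre to the vaccinated villages for 28 days after vaccination activities". That person is a key notifier of both adverse and serious adverse events. Caretakers are told to contact the community health worker or attend the health centre if there is a health problem, with no day limit.

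**The named risk.** Protocol 7.2.1 says that drawing 25 administrations from a 5-dose vial "may increase the risk of injection site reactions e.g. swelling and localised inflammation due to contamination", and adds that the preservative should minimise this. Protocol 9.4 notes that stoppers will be pierced more often than they are validated for, cites a stopper study, and rates the risk as minimal.

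**The concern.** Two problems meet here.

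First, the outcome definition in protocol 6.1 and the operational and analysis text disagree. From these documents, field staff cannot tell whether a mild injection-site infection seen on day 12 calls for an adverse event form. The analyst cannot tell whether such a form would belong in a table.

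Second, if the 7-day text governs, non-serious injection-site infections with onset on days 8 to 28 fall between the two outcomes: too late for one and not serious enough for the other. The protocol itself links local reactions to contamination of a vial used for more administrations than it was filled for. Mild local infections could be an early sign of that. They would be set aside while the people placed to receive such reports are still at the health centres. Protocol 9.5 accepts that passive surveillance may under-report and offers those dedicated staff as the mitigation. For non-serious events the 7-day limit gives up much of that mitigation.

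**Working it through.** **Passages side by side**

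| Place | Non-serious injection-site events | Serious events |
|---|---|---|
| Protocol 6.1 | 28 days (all adverse events) | 28 days |
| Objectives (synopsis, protocol 6, SAP 2.2) | 7 days | 28 days |
| Protocol section 8 | 7 days | 28 days |
| SAP 3.1.4 and 3.2.2 | 7 days | 28 days |
| SAP 4.3.3 | 7 days | no day limit restated |

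Protocol 6.1 stands alone. The texts also differ on what is timed: protocol section 8 and SAP 3.1.4 speak of events collected for 7 days, SAP 3.2.2 and 4.3.3 of events occurring within 7 days. An infection that starts on day 5 and is first seen on day 9 is in under one wording and arguably out under the other.

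**Tracing a case.** Take an injection-site infection with onset on day 10.
- If it leads to hospitalisation, is life-threatening or is an important medical event, it is a serious adverse event and is counted (protocol section 8, SAP 3.2.2.1).
- If it meets none of the seriousness criteria, it is outside the SAP 3.2.2 outcome and has no category in SAP 4.3.3.
- The uncounted period is 28 − 7 = 21 of the 28 staffed days, or 75%. This is a share of time, not of infections.

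**Figures in the plan that reproduce**
- Children targeted: 54 clusters × 2000 people × 30% = 32,400, as stated in protocol 7.1.
- Per vaccine arm: 27 × 600 = 16,200.
- Fractional doses per vial: 5 × 0.5 ml ÷ 0.1 ml = 25, as in protocol 7.2.

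**Illustration on assumed values.** The documents give neither an infection rate nor an onset distribution, so both are assumptions here. Uncounted cases in the fractional arm = 16,200 × rate × share starting after day 7, taking none as serious and all as reported:

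| Assumed rate | All cases | 0% late | 10% late | 30% late | 50% late |
|---|---|---|---|---|---|
| 0.01% | 1.62 | 0 | 0.16 | 0.49 | 0.81 |
| 0.05% | 8.1 | 0 | 0.81 | 2.43 | 4.05 |
| 0.1% | 16.2 | 0 | 1.62 | 4.86 | 8.1 |

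At an assumed 70% uptake the arm has 11,340 vaccinees, and the largest entry falls to 11,340 × 0.001 × 0.5 = 5.67.

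**Effect on a comparison of the vaccine arms.** Assume true rates of 0.05% (full) and 0.15% (fractional), 16,200 per arm, two-sided 5%, clustering ignored. Power = Φ(d/SE − 1.96), with SE = √[(p₀(1−p₀) + p₁(1−p₁))/n].
- No late cases: d = 0.0010, SE = 0.000351, d/SE = 2.85, power 81%.
- 10% late: 77%. 30% late: 66%.
- 50% late: d = 0.0005, SE = 0.000248, d/SE = 2.01, power 52%.

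The late share is taken as equal in both arms. Clustering would lower all four figures.

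**The case against.** The strongest reply is that 7 days is a deliberate choice. It is written into the objectives and repeated through both documents, with a longer window kept for events that matter more. Serious local infections are captured to day 28. The protocol judges the piercing risk to be minimal and relies on a preservative, a stopper study and the WHO multi-dose vial policy. The risk it names is swelling and localised inflammation, and nothing in the documents says that these start late. The same window applies to both vaccine arms, so it cannot by itself create a difference between them. Full against fractional dose is also not a prespecified safety test: protocol section 12 and SAP 4.3.3 compare the vaccine arms with control. Finally, surveillance is passive, so children are not being examined through day 28.

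Most of this stands, and it limits the point. A reader might infer that the trial misses later local infections in general, or that it could report no excess because it stopped counting. The documents do not support either. Serious cases are counted, and a difference between arms would be hidden only if contamination-related events tended to start later than ordinary reactions, which is not shown. Nor can any particular fraction of infections be called lost, since nil is within the range.

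Two things survive. A repeated choice does not remove the conflict with protocol 6.1. And a prior judgement that the risk is minimal does not settle the matter: about 16,200 targeted children per vaccine arm offer a chance to check it. Section 8 leaves adverse event definitions and grading to an SOP that is not among these documents, but it does not leave the window to that SOP.

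**Conclusion.** The point holds in a limited form. Protocol 6.1 contradicts the objectives, protocol section 8 and the SAP on how long non-serious adverse events are recorded, and the passages must be reconciled. If the SAP text governs, non-serious injection-site infections with onset on days 8 to 28 are not outcomes, even when they reach the stationed health professional.

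The size of the loss cannot be derived from the documents. The illustration runs from 0 to 8.1 uncounted fractional-arm cases and rests on assumed rates, assumed onset, full uptake and full reporting. Because the window is equal in both vaccine arms, the expected effect is fewer events and less precision, not bias. The primary carriage analysis is unaffected. This is a worthwhile, inexpensive improvement to safety ascertainment, and no evidence that the safety conclusions would be wrong.

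**What to change.** 1. Reconcile the recording window across protocol 6.1, the safety objective (protocol synopsis, protocol section 6, SAP 2.2), protocol section 8, and SAP 3.1.4, 3.2.2 and 4.3.3. Editing the SAP alone would leave the objectives and 6.1 in conflict with it. Extending one event type without rewording 6.1 would also leave the conflict, since 6.1 covers all adverse events.
2. Keep the 7-day summary of common local reactions as planned.
3. Add that any injection-site infection reported up to day 28 is recorded on the existing adverse event form with its onset date, and is tabulated separately for the full-dose and fractional-dose arms. Add a matching line to the tables in SAP 5.3. The denominators already exist: SAP 3.1.5 uses the number of children vaccinated from site records.
4. State whether each window refers to onset or to the date of reporting.

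The cost is wording and a few more forms, with no additional staff or visits, because the health professional and community health workers are already in place to day 28. The downside is that some unrelated background skin infections will be recorded. They would occur in both vaccine arms, and the separate table keeps them out of the 7-day summary.
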